5.6 Other Modalities or Procedures

No other treatment modalities (i.e., radiation or surgery) will be part of MCD treatment included in this protocol as they are not standard of care therapies for MCD.

5.7 Duration of Therapy

In the absence of treatment delays due to AEs, treatment may continue for **4 weekly doses** or until one or more of the following occur:

- Disease progression
- Inter-current illness that prevents further administration of treatment
- Unacceptable AE(s)
- Pregnancy
- Subject decides to withdraw from study treatment
- General or specific changes in the subject's condition render the subject unacceptable for further treatment in the judgment of the investigator

5.8 Duration of Follow Up

For determination of study endpoints, all subjects will be followed for up to 24 months or until death, whichever occurs first after removal from study treatment.

Subjects removed from study treatment for unacceptable AEs will be followed for resolution or stabilization of the AE(s). All subjects (including those withdrawn for AEs) should be followed after removal from study treatment as stipulated in the protocol.

Although study follow-up is for 24 months, patients will be consented to be contacted at 30, 36, 42, 48, 54, and 60 months simply to assess vital status after completion of study procedures.

5.9 Study Withdrawal

Subjects will be removed from the study, removed from protocol mandated therapy (i.e. further therapy will be at discretion of the treating provider), and the study PI notified when any of the criteria listed in section 5.7 apply. The reason for discontinuation of protocol therapy will be documented in the electronic case report form (eCRF).

If a subject decides to withdraw from the study (and not just from protocol therapy) an effort will be made to complete and report study assessments as thoroughly as possible. At the time of withdrawal, the investigator will attempt to establish as completely as possible the reason for the study withdrawal.

- The subject will be asked if they are willing to allow for the abstraction of relevant information from their medical record in order to meet long-term follow-up objectives (e.g., survival) outlined in the protocol.
- A complete final evaluation at the time of the subject's study withdrawal will be obtained with an explanation of why the subject is withdrawing from the study.
- If the subject is noncompliant and does not return for an end of study follow up assessment, this will be documented in the eCRF.
- If the reason for removal of a subject from the study is an AE, the principal specific event will be recorded in the eCRF.

Excessive subject withdrawals from protocol therapy or from the study can render the study un-interpretable; therefore, unnecessary withdrawal of subjects should be avoided.

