3.0 STUDY ENDPOINTS

3.1 Primary Endpoint

Safety will be classified and graded by non-hematologic Grade ≥ 3 AEs (CTCAE v5.0) and treatment-related mortality through twelve weeks from the start of rituximab with or without etoposide therapy.

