5.3 Toxities and Dosing Delays/Dose Modifications

Any patient who receives treatment on this protocol will be evaluable for toxicity. Each patient will be assessed periodically for the development of any toxicity according to the Time and Events table (Section 8.1). Toxicity will be assessed according to the National Cancer Institute (NCI) CTCAE, v5.0. Dose adjustments should be made according to the system showing the greatest degree of toxicity. See **Tables 2-4** below for recommended dose delays/dose modifications.

Assigning cause of death is often difficult in Malawi because diagnostic capabilities are limited and deaths frequently occur outside of health facilities. To address this challenge, two senior non-study clinicians will be enlisted to review all study data for deceased patients and assign cause of death as either likely treatment-related, MCD-related, related to another cause, or unable to determine. In the event of discordant conclusions, a third senior clinician will serve as a tiebreaker.

Table 2: Hematological toxicity dose reductions		
ANC	Platelets	Action
≥ 0.5 x 10 ³ /µL	≥ 50 x 10 ³ /µL	None.

$< 0.5 \times 10^3/\mu\text{L}$	$< 50 \times 10^3/\mu\text{L}$	
FIRST EPISODE: Hold current etoposide dose until ANC $\geq 0.5 \times 10^3/\mu\text{L}$ and platelets $\geq 50 \times 10^3/\mu\text{L}$. Restart next treatment at 75 mg/m^2. Do NOT hold or reduce rituximab dose.
 
SECOND EPISODE: Hold current etoposide dose until ANC $\geq 0.5 \times 10^3/\mu\text{L}$ and platelets $\geq 50 \times 10^3/\mu\text{L}$. Restart next treatment at 50 mg/m^2. Do NOT hold or reduce rituximab dose.
 
Goal is to replace doses and complete full course of four doses of both etoposide and rituximab.

---------------------------------	--------------------------------	--

Table 3: Non-hematological toxicity dose reductions for rituximab	
NCI CTC Grade	
0-2	No change from original dose.
3-4	Wait until resolved to \leq Grade 2, no dose reduction.
Second episode of Grade 3 or 4 toxicity	Hold until resolved to \leq Grade 2, no dose reduction.
Third episode of Grade 3 or 4 toxicity	Remove subject from trial

Table 4: Hepatic and renal dysfunction dose adjustment for etoposide	
Event	Action
Renal dysfunction	
Cr clearance $>50 \text{ ml/min}$	None
Cr clearance 15-50 ml/min	Decrease dose to 75 mg/m^2
Cr clearance $<15 \text{ ml/min}$	Decrease dose to 50 mg/m^2
Hepatic dysfunction	
Bilirubin $<1.5 \text{ mg/dL}$	None

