9.4 Adverse Event Reporting

9.4.1 IRB Reporting Requirements:

UNC:

- The UNC IRB will be notified of all SAEs that qualify as an Unanticipated Problem as per UNC IRB policy using the IRB's web-based reporting system within 7 days of the Investigator becoming aware of the problem. Please note, these events must be reported to the sponsor within 24 hours of learning of the occurrence.

Pregnancy:

- Pregnancies and suspected pregnancies (including a positive pregnancy test regardless of age or disease state) of a female subject occurring while the subject is on study, or within 30 days of the subject's last dose of study drug should be recorded as SAEs. The subject is to be discontinued immediately from the study.
- The female subject should be referred to an obstetrician-gynecologist, preferably one experienced in reproductive toxicity for further evaluation and counseling.

- The Investigator will follow the female subject until completion of the pregnancy and must document the outcome of the pregnancy (either normal or abnormal outcome) and report the condition of the fetus or newborn to the UNC study coordinator. If the outcome of the pregnancy was abnormal (e.g., spontaneous or therapeutic abortion), the investigator should report the abnormal outcome as an AE. If the abnormal outcome meets any of the serious criteria, it must be reported as an SAE.

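### Sections 5.9, 9.4.1 and Table 3 take subjects out of the study where 5.8 requires follow-up to 24 months, leaving some 12-week safety events and OS at risk of going unrecorded

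*Combined protocol and SAP*

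**What the plan says.** Section 5.7 gives the course as four weekly doses "or until one or more of the following occur", followed by progression, intercurrent illness, unacceptable adverse events, pregnancy, the subject's decision to leave study treatment, and a change in condition. All are reasons to stop treatment.

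Section 5.9 then attaches a wider consequence to the same list: "Subjects will be removed from the study, removed from protocol mandated therapy", "when any of the criteria listed in section 5.7 apply". Table 3 in Section 5.3, at the third episode of Grade 3 or 4 non-hematologic toxicity, reads "Remove subject from trial". The pregnancy text in 9.4.1 reads "The subject is to be discontinued immediately from the study".

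Section 5.8 says otherwise: "For determination of study endpoints, all subjects will be followed for up to 24 months or until death", counted after removal from study treatment, and "All subjects (including those withdrawn for AEs) should be followed after removal from study treatment as stipulated in the protocol".

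The primary endpoint in Section 3.1 covers non-hematologic Grade 3 or higher events and "treatment-related mortality through twelve weeks from the start of rituximab with or without etoposide therapy". Sections 3.2.2 and 3.2.3 assess OS and EFS at 12 weeks, one year and two years.

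**The concern.** A site with a patient who progresses after the second dose has two instructions. Section 5.9 takes the patient out of the study; Section 5.8 keeps the patient under follow-up. Which one the site obeys decides whether a death or a severe event at week 9 enters the primary analysis.

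Leaving for progression or intercurrent illness is not random with respect to outcome. The trial tests safety in 24 evaluable patients with a cut-off of six, and the early monitoring boundary for treatment-related mortality in Table 8 is two deaths. At that size, one or two unrecorded patients can change a conclusion.

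**Working it through.** **Step 1. The plan's own figures.** Section 10.2 gives n = 24, null rate 40%, expected rate 20%, one-sided exact alpha 0.1, and safety declared with six or fewer patients with an event. With X ~ Binomial(24, p):

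- P(X ≤ 6 | p = 0.40) = 0.096, within 0.1.
- P(X ≤ 6 | p = 0.20) = 0.811, matching the stated 80%.
- P(X ≤ 7 | p = 0.40) = 0.192, so six is the largest valid cut-off.

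The sample size calculation reproduces and is not in dispute.

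**Step 2. Do other sections settle the conflict?**

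| Place | What it provides | Does it resolve the conflict? |
|---|---|---|
| 5.9, bracket and second paragraph | The bracket speaks only of further therapy; the next paragraph separates leaving the study from leaving therapy | Suggests that therapy was meant, but the opening words name both |
| 5.9, record abstraction | Written for a subject who decides to withdraw | Does not cover removal by rule |
| Table 7, footnote on the end-of-treatment visit | A withdrawn subject completes that visit, 7 to 14 days after the final dose | Names no later visit for this subject |
| Table 7, toxicity footnote | Toxicity assessed through week 12 and again at 24 months | Does not say whether removed subjects are included |
| 9.2 and 9.3.1 | AE and SAE recording to 30 days after treatment ends | Stops before week 12 |
| 10.5.2 | Loss to follow-up counts as failure for EFS and OS; defined as no phone contact for three months | Does not mention removal by rule |

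The AE window can be dated. With the last dose on day 22, recording ends on day 22 + 30 = day 52. If treatment stops after the day 1 or day 8 dose, it ends on day 31 or day 38. The primary window runs to 12 × 7 = day 84.

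**Step 3. Which events are exposed if 5.9 is followed?**

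- *Table 3 removals.* The patient has already had three Grade 3 or 4 episodes, so the patient-level AE event is counted. Later treatment-related death and survival are exposed.
- *Unacceptable AE.* Usually already counted, provided that the event was non-hematologic and Grade 3 or higher.
- *Progression.* Normally already an EFS event. OS, treatment-related death and a first Grade 3 or higher event up to week 12 are exposed.
- *Intercurrent illness or another non-toxicity reason.* The same 12-week safety outcomes, OS, and also EFS.

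**Step 4. Illustration of size.** The documents give no share of events lost, so the shares below are assumptions. Section 8.3 keeps anyone with one dose evaluable for toxicity, so the denominator stays at 24.

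If each event goes unrecorded with probability q, the observed rate is 0.40 × (1 − q):

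| q | Observed rate | P(X ≤ 6 given n = 24) |
|---|---|---|
| 0 | 0.400 | 0.096 |
| 2% | 0.392 | 0.110 |
| 5% | 0.380 | 0.134 |
| 10% | 0.360 | 0.182 |

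If exactly one patient with an event goes unrecorded, safety is declared whenever the true count is seven or fewer: P(X ≤ 7 | 24, 0.40) = 0.192. For scale, 24 × 0.40 = 9.6 events are expected, so 10% is about one patient.

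For treatment-related mortality, one unrecorded death would turn 1/24 = 4.2% (exact 95% CI 0.1% to 21.1%) into 0/24 (0% to 14.2%).

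**The case against.** The strongest defence is that Section 5.8 governs follow-up, states its purpose as determining the endpoints, and expressly includes those withdrawn for AEs. Section 5.9 can be read in harmony with it, since its bracket and its next sentence concern therapy. If sites follow 5.8, nothing is lost. That stands as a limit on the impact. It does not remove the conflict, because the opening of 5.9 lists study and therapy as separate removals and its second paragraph shows that the distinction was known.

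A second defence is that the route to a hidden AE is narrow. It needs an early stop for a reason other than toxicity, no earlier Grade 3 or higher event, and a first event after the 30-day window but before week 12. Anyone who completes four doses is outside the 5.7 list. This also stands, and it is why the illustration stops at 10%.

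A reader might infer that toxicity removals broadly hide primary AE events and that 10% or 20% of first events would vanish. The documents do not support this: the event that triggers removal is usually itself the primary event, and no share lost is given anywhere. A reader might also infer that survival would be biased upward. That is not established. Section 10.5.2 counts loss to follow-up as failure, which pushes estimates down, and it does not say how a subject removed by rule is handled.

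The pregnancy text is the weakest of the three citations, since 9.4.1 goes on to require follow-up to the pregnancy's outcome. It still needs to agree with 5.8.

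**Conclusion.** The contradiction is in the text and should be resolved: 5.9, Table 3 and 9.4.1 end study participation where 5.8 continues it. The exposure is conditional on sites following 5.9. It then falls mainly on treatment-related death to week 12, OS, and first Grade 3 or higher non-hematologic events in patients who stop early for progression, intercurrent illness or another non-toxicity reason. EFS in patients who progress, and AEs that trigger removal, are largely protected.

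The size cannot be derived from the documents. Under the stated assumptions (true rate 40%, n = 24, cut-off six), the false-safe probability rises from 0.096 to 0.192 with one patient's event unrecorded, and to about 0.11 to 0.18 with 2% to 10% of events unrecorded. Unrecorded events can only lower the observed AE and treatment-related mortality counts; the direction of any OS bias is uncertain.

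**What to change.** Reconcile 5.8, 5.9, Table 3 and 9.4.1 so that meeting a 5.7 or Table 3 criterion ends protocol therapy only. State that, unless the subject withdraws consent to follow-up, the subject stays on the Table 7 schedule for the 12-week safety endpoint and for EFS and OS to 24 months. The 9.4.1 wording should make the same distinction between therapy and follow-up.

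Those edits alone would not secure AE capture to week 12. Also align the 30-day AE and SAE recording windows in 9.2 and 9.3.1 with the 12-week primary window, and amend the Table 7 end-of-treatment footnote so that it does not read as the last visit for a withdrawn subject.

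The cost is an amendment to wording in these places, plus AE and SAE recording for some weeks beyond the present 30 days. The 12-week visit, its toxicity evaluation and the 24-month follow-up are already planned. No treatment-stopping rule changes, and the sample size stands.

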6.0 DRUG INFORMATION

6.1 Rituximab

Rituximab for this study will be supplied as Reditux ([name], India). For extensive product information, preparation instructions, and AEs information, please refer to the United States Food and Drug Administration product guidelines

here:

https://www.accessdata.fda.gov/drugsatfda_docs/label/2010/103705s5311lbl.pdf

Rituximab is the standard therapy for MCD in HIC, but published data is missing on the safety of rituximab in SSA. Rituximab will be provided free of charge to all study participants.

6.1.1 Description

Rituximab is a genetically engineered chimeric murine/human monoclonal IgG1 kappa antibody directed against the CD20 antigen. Rituximab has an approximate

molecular weight of 145 kD. Rituximab has a binding affinity for the CD20 antigen of approximately 8.0 nM. It is produced by mammalian cell (Chinese Hamster Ovary) suspension culture in a nutrient medium containing the antibiotic gentamicin. Gentamicin is not detectable in the final product.

6.1.2 Storage and Handling

Rituximab should be stored at 2-8°C. Do NOT freeze or store at room temperature. The product is a protein. HANDLE GENTLY AND AVOID FOAMING. The avoidance of foaming during product handling, preparation and administration is important, as foaming may lead to the denaturing of the product proteins.

6.1.3 Pharmacology

Pharmacokinetics: In prior studies patients treated at the 375 mg/m² dose levels exhibited detectable antibody concentrations throughout the treatment period. Most patients exhibited increasing pre-infusion antibody concentrations with each subsequent infusion. In nine patients, the T_{1/2} following the first antibody infusion was 59.8 hours (11.1-104.6 hr) with a C_{max} of 271mcg/mL. Following the fourth antibody infusion when circulating B cells had been depleted and antigenic sites coated, the T_{1/2} was 174 hr (26.4-442.3 hr) and C_{max} 496.7 mcg/mL.

Duration: Detectable in serum 3-6 months after treatment completion; B-cell recovery begins almost 6 months following treatment completion; median B-cell levels return to normal by 12 months following treatment completion.

Absorption: Intravenous: Immediate and results in a rapid and sustained depletion of circulating and tissue-based B cells.

Half-life elimination: Median terminal half-life: 22 days (range: 6-52 days)

Excretion: Uncertain; may undergo phagocytosis and catabolism in the reticuloendothelial system (RES).

6.1.4 Formulation

100 mg (10 mL) and 500 mg (50 ml) pharmaceutical grade vials at a concentration of 10 mg of protein per mL (actual concentration should be noted on the product label).

6.1.5 Return and Retention of Study Drug

Return and retention of rituximab will be done per UNC Project Malawi drug destruction SOP used in support of ongoing and completed clinical trials.

6.1.6 Adverse Events Associated with Investigational Drug

Human Toxicology: Single doses of up to 2275 mg/m² and weekly x 4 doses of 375 mg/m² have been administered without dose limiting toxicity. AEs are most common during the initial antibody infusion and usually consist of Grade 1 or 2 fever (73%), asthenia (16%), chills (38%), nausea (19%), vomiting (11%), rash (14%) and tumor site pain (3%). Grade 1 or 2 hypotension (8%) may be treated

with IV fluids. Hematologic toxicity is usually mild and reversible. Transient decreases in the WBC or platelet count have been observed - especially in patients with high levels of circulating tumor cells or bone marrow involvement. Two patients have had late-onset Grade 4 neutropenia at four and ten months that was attributed to an unknown cause, was transient, and resolved. Infections (Grade 1 and 2) have not been related to dose level. Symptoms are generally associated with the initial antibody infusions and diminish in frequency with each successive infusion. A report in the literature described an increase in fatal infection in HIV-related lymphoma patients when rituximab was used in combination with CHOP chemotherapy as compared to CHOP alone.

Severe Infusion and Hypersensitivity Reactions: Rituximab has caused severe infusion reactions. In some cases, these reactions were fatal. An infusion-related symptom complex consisting of fever and chills/rigors has occurred in many patients during the first rituximab infusion. Signs and symptoms of severe infusion reactions may include urticaria, hypotension, angioedema, hypoxia, or bronchospasm. The most severe manifestations and sequelae include pulmonary infiltrates, acute respiratory distress syndrome, myocardial infarction, ventricular fibrillation, cardiogenic shock, and anaphylactic and anaphylactoid events. These reactions generally occurred within 30 minutes to 2 hours of beginning the first infusion, and resolved with slowing or interruption of the rituximab infusion and with supportive care (including, but not limited to IV saline, diphenhydramine, and acetaminophen).

Tumor Lysis Syndrome: Rituximab rapidly decreases benign and malignant CD20 positive cells. Tumor lysis syndrome has been reported to occur within 12 to 24 hours after the first rituximab infusion in patients with high numbers of circulating malignant lymphocytes. Patients with high tumor burden (bulky lesions) may also be at risk. Patients at risk for developing tumor lysis syndrome should be followed closely and appropriate laboratory monitoring performed.

Hepatitis B Reactivation with Related Fulminant Hepatitis and Other Viral Infections: Hepatitis B virus (HBV) reactivation with fulminant hepatitis, hepatic failure, and death has been reported in some patients with hematologic malignancies treated with rituximab. The majority of patients received rituximab in combination with chemotherapy. The median time to diagnosis of hepatitis was approximately four months after the initiation of rituximab and approximately one month after the last dose. Persons at high risk of HBV infection should be screened before initiation of rituximab. Carriers of hepatitis B should be closely monitored for clinical and laboratory signs of active HBV infection and for signs of hepatitis during and for up to several months following rituximab therapy. In patients who develop viral hepatitis, rituximab and any concomitant chemotherapy should be discontinued and appropriate treatment, including antiviral therapy, initiated. There are insufficient data regarding the safety of resuming rituximab therapy in patients who develop hepatitis subsequent to HBV reactivation. The following additional serious viral infections, either new, reactivated or exacerbated, have been identified

in clinical studies or postmarketing reports. The majority of patients received rituximab in combination with chemotherapy or as part of a hematopoietic stem cell transplant. These viral infections included John Cunningham virus, which is associated with progressive multifocal leukoencephalopathy, cytomegalovirus, herpes simplex virus, parvovirus B19, varicella zoster virus, West Nile virus, and hepatitis C. In some cases, the viral infections occurred up to one year following discontinuation of rituximab and have resulted in death.

Severe Mucocutaneous Reactions: Mucocutaneous reactions, some with fatal outcome, have been reported in patients treated with rituximab. These reports included paraneoplastic pemphigus (an uncommon disorder which is a manifestation of the patient's underlying malignancy), Stevens-Johnson syndrome, lichenoid dermatitis, vesiculobullous dermatitis, and toxic epidermal necrolysis. The onset of the reaction in reported cases have varied from 1-13 weeks following rituximab exposure. Patients experiencing a severe mucocutaneous reaction should not receive any further infusions and seek prompt medical evaluation. Skin biopsy may help to distinguish among different mucocutaneous reactions and guide subsequent treatment. The safety of readministration of rituximab to patients with any of these mucocutaneous reactions has not been determined.

Bowel Obstruction and Perforation: Abdominal pain and bowel obstruction and perforation (in some cases leading to death) were observed in patients receiving rituximab in combination with chemotherapy for DLBCL. In post-marketing reports, which included patients with both low-grade or follicular NHL and DLBCL, the mean time to onset of symptoms was 6 days (range 1-77) in patients with documented gastrointestinal perforation. Complaints of abdominal pain, especially early in the course of treatment, should prompt a thorough diagnostic evaluation and appropriate treatment.

Cardiovascular: The incidence of serious cardiovascular events in the double-blind clinical trial for rheumatoid arthritis (RA) patients was 1.7% and 1.3% in rituximab and placebo groups, respectively. Three cardiovascular deaths occurred during the double-blind period of the RA studies, including all rituximab regimens (3/759 = 0.4%) as compared to none in the placebo group (0/389).

Since patients with RA are at increased risk for cardiovascular events compared to the general population, patients with RA should be monitored throughout the infusion and rituximab should be discontinued in the event of a serious or life-threatening cardiac event. Rituximab infusions should be discontinued in the event of serious or life-threatening cardiac arrhythmias. Patients who develop clinically significant arrhythmias should undergo cardiac monitoring during and after subsequent infusions of rituximab. Patients with pre-existing cardiac conditions including arrhythmias and angina have had recurrences of these events during rituximab therapy and should be monitored throughout the infusion and immediate post-infusion period.

Renal: Rituximab administration has been associated with severe renal toxicity including acute renal failure requiring dialysis and, in some cases, has led to fatal outcomes in hematologic malignancy patients. Renal toxicity has occurred in patients with high numbers of circulating malignant cells ($> 25,000/\mu\text{L}$) or high tumor burden who experience tumor lysis syndrome and in patients with NHL administered concomitant cisplatin therapy during clinical trials. The combination of cisplatin and rituximab is not an approved treatment regimen. If this combination is used in clinical trials *extreme caution* should be exercised; patients should be monitored closely for signs of renal failure. Discontinuation of rituximab should be considered for those with rising serum creatinine or oliguria.

Immunization: The safety of immunization with live viral vaccines following rituximab therapy has not been studied and vaccination with live virus vaccines is not recommended. The ability to generate a primary or anamnestic humoral response to vaccination is currently being studied. For patients with NHL, the benefits of primary and/or booster vaccinations should be weighed against the risks of delay in initiation of rituximab therapy.

Carcinogenesis, Impairment of Fertility, Pregnancy, and Nursing: No long-term animal studies have been performed to establish the carcinogenic potential of rituximab. Studies also have not been completed to assess mutagenic potential of rituximab, or to determine potential effects on fertility in males or females. Individuals of childbearing potential should use effective contraceptive methods during treatment and for up to 12 months following rituximab therapy. It is not known whether rituximab is excreted in human milk. Because human IgG is excreted in human milk and the potential for absorption and immunosuppression in infants is unknown, women should be advised to discontinue nursing until circulating drug levels are no longer detectable.

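### Table 3 lets rituximab continue at full dose after a first or second Grade 3-4 non-hematologic toxicity, with no exception for the events where Section 6.1.6 or Appendix D says to stop

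*Combined protocol and SAP*

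**What the plan says.** Section 5.3 points the clinician to Tables 2-4 "below for recommended dose delays/dose modifications". Table 3 is titled "Non-hematological toxicity dose reductions for rituximab" and is not limited to particular events. Its rows run as follows:

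- Grades 0-2: the dose is unchanged.
- Grade 3-4: wait for recovery to "Grade 2, no dose reduction".
- "Second episode of Grade 3 or 4 toxicity": hold for the same recovery, again with no reduction.
- "Third episode of Grade 3 or 4 toxicity": the subject leaves the trial.

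Section 6.1.6, under severe mucocutaneous reactions, says: "Patients experiencing a severe mucocutaneous reaction should not receive any further infusions". It adds: "The safety of readministration of rituximab to patients with any of these mucocutaneous reactions has not been determined". Neither sentence depends on recovery or on an episode count. On timing it says: "The onset of the reaction in reported cases have varied from 1-13 weeks following rituximab exposure".

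Three other stop instructions also lie outside Table 3. Section 6.1.6 directs that rituximab be discontinued in patients who develop viral hepatitis, and that infusions be discontinued for serious or life-threatening arrhythmia. The reinfusion column of Appendix D says not to resume after a Grade 3 (severe) hypersensitivity reaction.

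Section 5.7 lists general reasons to end treatment, including an unacceptable adverse event, intercurrent illness and investigator judgment. Section 5.9 requires removal from protocol therapy once any of them applies.

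**The concern.** Clinicians turn to a dose-modification table when a toxicity occurs. Table 3 does not use the word 'resume'. But a hold until recovery, no reduction, and removal only at the third episode can only mean that the remaining doses are given in full. For a severe mucocutaneous reaction that is the opposite of what the drug section directs.

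Section 6.1.6 includes Stevens-Johnson syndrome and toxic epidermal necrolysis in this class and notes that some reactions were fatal. The stake is re-exposure of a patient whom the protocol itself says should not be re-exposed. Whether that is avoided depends on someone recalling 6.1.6, or judging the event unacceptable under 5.7, against the direction of the table in front of them.

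**Working it through.** The protocol states no figure on this point. The check is a comparison of texts, followed by a rough size.

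**Texts side by side (first or second episode, improved to Grade 2 or lower)**

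| Event | Table 3 | Elsewhere in the protocol |
|---|---|---|
| Severe mucocutaneous reaction | Continue, full dose | 6.1.6: no further infusions |
| Viral hepatitis | Continue, full dose | 6.1.6: discontinue; too few data on the safety of resuming after hepatitis B reactivation |
| Serious or life-threatening arrhythmia | Continue, full dose | 6.1.6: discontinue infusions |
| Grade 3 hypersensitivity | Continue, full dose | Appendix D: do not resume |

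The first row assumes that 'severe' means Grade 3 or higher. The documents do not map the word to a CTCAE grade for these reactions, although Appendix D labels its Grade 3 as severe. The hepatitis and arrhythmia rows likewise suppose an event graded 3 or 4.

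The conflict is plainest in the first row. For arrhythmia, 6.1.6 also speaks of monitoring during later infusions after clinically significant arrhythmias. Appendix D does not say whether its bar extends to later weekly doses.

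Sections 5.3, 5.4.9, 5.7, 5.9 and Appendix D contain no statement that one of these texts overrides Table 3. The general requirement in 11.4 to follow the protocol does not settle it, because both texts are in the protocol.

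**Size for mucocutaneous reactions**

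Inputs from the documents: doses on days 1, 8, 15 and 22 (5.2); a visit window of 7 days either way (8.1, footnote 2); onset 1 to 13 weeks after exposure (6.1.6); 27 patients (10.2).

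Assumptions not in the documents: incidence at any time of 0.1% to 1%; onset uniform over the range; weeks counted from the first dose.

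- Onset range: day 1 + 7 = 8 to day 1 + 91 = 92, a width of 84 days.
- Share with onset before the last dose: (day of last dose − 8) / 84.
 - Last dose on day 22: 14/84 = 16.7%.
 - Last dose delayed to day 29: 21/84 = 25%.
 - Last dose brought forward to day 15: 7/84 = 8.3%.
- Expected patients = 27 × incidence × share. Chance of at least one = 1 − (1 − incidence × share)^27.

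| Incidence | Share | Expected patients | Chance of at least one |
|---|---|---|---|
| 0.1% | 7/84 | 0.002 | 0.2% |
| 0.1% | 14/84 | 0.0045 | 0.4% |
| 1% | 14/84 | 0.045 | 4.4% |
| 1% | 21/84 | 0.0675 | 6.5% |

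One expected patient would need an incidence before the last dose of 1/27 = 3.7%.

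These figures count onset only. Table 3 calls for another dose only if the patient survives and improves to Grade 2 or lower, so the number re-dosed would be smaller. If the weeks run from the most recent dose, onset before the last dose is possible only on a dosing day or during a delay, and the case is rarer still.

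For a patient who is affected, Table 3 would continue with 3 × 375 = 1125, 2 × 375 = 750 or 1 × 375 = 375 mg/m², depending on whether onset precedes dose 2, 3 or 4.

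**Size for the other events**

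The documents do not support a useful estimate. For hepatitis, the reported median time to diagnosis in 6.1.6 falls after the last dose. For hypersensitivity, the one local figure is a single Grade 3 reaction among ten compassionate-use patients (1.5). At face value that is 27 × 1/10 = 2.7 patients, but the exact 95% interval for 1 of 10 is 0.3% to 44.5%, so nothing here rests on it.

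**The case against.** The strongest reply is that the correct instruction is already in the protocol. A specific prohibition beside a general recommendation is normally read as an exception. The protocol places several event-specific stop rules outside Table 3, which suggests that the table was meant as a default. Stevens-Johnson syndrome or toxic epidermal necrolysis would very likely be a serious adverse event, notified within 24 hours (9.3.2) under continuous safety monitoring (9.5). Re-dosing would then need several people to overlook 6.1.6. For hypersensitivity, Section 5.4.9 sends the clinician directly to Appendix D.

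Most of this stands, and it limits the point. A reader might infer that the protocol obliges investigators to rechallenge these patients, or leaves them no way to stop. The documents do not support that: Table 3 is only recommended, and 5.7 with 5.9 provides a route that becomes mandatory once the investigator judges that a criterion applies. A reader might also infer that only mucocutaneous reactions need an exception. That is too narrow, and a footnote naming them alone could suggest that the other stop rules do not override the table.

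The reply does not remove the conflict. 'Unacceptable' is undefined, and Table 3 itself treats first and second Grade 3-4 events as ones after which dosing continues. The precedence of the specific rule has to be inferred, because it is nowhere written.

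**Conclusion.** The point holds as a gap in the dose table. For four kinds of event that the protocol elsewhere treats as reasons to stop, Table 3 read alone says to continue after recovery, and no text says which instruction governs. The finding about the wording is firm; the practical consequence is uncertain and, for mucocutaneous reactions, rare. Well below one patient of 27 is expected, given the assumed incidence and uniform onset and with 'severe' read as Grade 3 or higher.

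It would be wrong to infer a threat to the trial's result. Nothing in the sample size, the decision rule or the analysis depends on this wording, and a patient with such a reaction has already had a Grade 3 or higher non-hematologic event. The change should be made because the events can be fatal and the correction costs almost nothing.

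**What to change.** Add a footnote to Table 3:

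> Event-specific discontinuation rules in 6.1.6 and Appendix D take precedence over this table. Rituximab is permanently discontinued for a severe (Grade 3 or higher) mucocutaneous reaction, and is stopped as those sections direct for viral hepatitis, serious or life-threatening arrhythmia and Grade 3 hypersensitivity, regardless of episode count or resolution to Grade 2 or lower.

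This adds no new clinical rule beyond fixing the grade meant by 'severe'. It puts existing instructions where dosing decisions are made. The cost is one footnote in the next amendment, with no change to sample size, visits, data collection or analysis.
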